	Visit 1 Week -3 to 0	Visit 2 Week 0	Visit 3 Week 4	Visit 4 Week 8	Visit 5 Week 12	Visit 6 Week 16	Visit 7 Week 20	Visit 8 Week 24	Visit 9 Week 28	Visit 10 Week 32	Visit 11 Week 36	Termination visit Week 40 / Drop-out Visit	Unscheduled Visit
Informed consent	X												
Eligibility criteria	X												
Demographic and baseline characteristics	Х												
Med. hist./Prior medication	X												
Standard ECG	X												
Pregnancy test	X											X	
Blood for viral markers	X											Х	
Blood sample for D-dimers	X												
Randomization		X ²											
Physical examination ²	X		Х			Х			Х			Х	Х
Vital signs³	X	Х	Х	Х	Х	Х	Х	Х	Х	Х	Х		Х
Body weight ²	X					Х			Х				
Safety laboratory ²	X	X	Х	X	Х	Х	Х	Х	Х	Х	X	Х	Х
Serum IgG ²	X	Х	Х	Х	Х	Х	Х	Х	Х	Х	Х	Х	Х
Enzymes ²	X	X	Х	Х	Х	Х			Х			Х	Х
Biomarkers blood sample	X					Х						Х	
Blood sample for additional safety lab ⁵		Х				Х			Х			Х	
Direct Coombs' test⁵		X				X			X			X	
CSM for TIS determination ²	X	X	Х	Х	Х	Х			Х			X	X
CDASI ²		Х	Х	Х	Х	Х			Х			Х	X
SF-36 Health Survey ²		X	_			Х						Х	
Wells score for DVT ⁴	Х	Х	Х	Х	Х	Х	Х	Х	Х	Х	X		Х
Wells score for PE⁴	Х	X	Х	Х	Х	Х	Х	Х	Х	Х	X		Х
Infusion of IMP ¹		X*	X*	X*	X*	X**	X**	X**	X*	X*	Χ#		
Adverse event monitoring		Throughout the study											
Concomitant medication			Throughout the study										

¹ Infusion cycles can last between 2 to 5 days, consisting of 2 or more infusion episodes.

²Before IMP administration;

³ Before, during and after each infusion episode;

⁴ At screening and after each infusion cycle;

⁵ Before and after infusion cycle;

^{*}Blinded infusion of either placebo or 2.0 g/kg Octagam 10%

^{**}Unblinded infusions of 2.0 g/kg Octagam 10%;

[figure not shown]
[#]In case subject is stable on the 2.0 g/kg Octagam 10% dose, they can be switched to 1.0 g/kg Octagam 10%, at the discretion of the investigator

[name]

[name]

PROTOCOL SIGNATURES

This study is intended to be conducted in compliance with the protocol, Good Clinical Practice and applicable regulatory requirements.

Clinical Project Manager Signature Date

Octapharma Pharmazeutika Produktionsges.m.b.H.

[name]

Manager Biometrics

Signature

Date

18 June 2019

Date

Octapharma Pharmazeutika Produktionsges.m.b.H.

Version 12 18-Jun-2019

PROTOCOL SIGNATURES

This study is intended to be conducted in compliance with the protocol, Good Clinical Practice and applicable regulatory requirements.

Signature

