3.3 Discussion of Study Design and Choice of Control Group

3.3.1 Study Design

The study design of ProDERM includes all major scientific, state-of-the-art interventions needed to assess the efficacy, safety and tolerability of therapeutic treatments in DM patients.

The total observation period of the study is 40 weeks. For a proper assessment of efficacy, clinical experience has shown that at least 4 treatment cycles are necessary to be documented. This resulted in a duration of 16 weeks for the first (controlled) phase of the study. An active treatment phase of 6 months (24 weeks) is recommended by the International Myositis Assessment and Clinical Studies Group.[32]

In order to minimize the risk for subjects in the **placebo arm**, a conditional switch to active treatment is introduced in the (blinded) First Period: All subjects in the placebo arm who deteriorate at 2 consecutive visits until Week 8 or after Week 8 will be switched to 2.0 g/kg (20 mL/kg) of Octagam 10%. In case of further, confirmed deterioration on the Octagam 10% treatment, subjects will drop-out.

In contrast, subjects in the 2.0 g/kg (20 mL/kg) **Octagam 10% arm** will receive placebo if they deteriorate at 2 consecutive visits until Week 8 or after Week 8. In case of confirmed deterioration after the switch to placebo, subjects will eventually drop-out. Subjects who did not deteriorate after the switch to placebo at 2 consecutive visits will automatically drop out at Week 16. This procedure was introduced to maintain the blinding of treatment.

In the Extension Period of the study, subjects will receive 6 infusion cycles of 2.0 g/kg (20 mL/kg) of Octagam 10% every 4 weeks. If the subject is stable on the 2.0 g/kg (20 mL/kg) dose, the investigator may decide on a case by case basis, if they want to treat the subject with the lower dose of 1.0 g/kg (10 mL/kg) Octagam 10%, starting at Week 28. Thereby, data on long-term efficacy and tolerability will be generated.

The 4-week interval between infusions has been chosen to make results comparable to the old Dalakas study [4] and to stay in line with current clinical practice.

Immunosuppressive agents and corticosteroids are allowed if stable dosages are not exceeded (see Section 4.2.1) in order to comply with the EFNS Guidelines saying that IGIV is recommended as a second-line treatment. [6]

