6.1.2 Visit 2 (Week 0; Baseline of First Period)

Subjects who are eligible will visit the study site and enter the controlled phase (First Period) after randomization.

Visit 2 should take place within 3 weeks after the Screening Visit.

All eligible subjects will receive their first infusion of either 2.0 g/kg (20 mL/kg) Octagam 10% or placebo as per randomization. The following assessments will be performed:

Before infusion cycle:

- Randomization and enrollment into the double-blind treatment period.
- SF-36v2.
- Vital signs.
- Blood sample for safety laboratory (hematology and clinical chemistry).
- Blood sample for additional safety lab parameters "Panel 1" (serum haptoglobin and plasma-free hemoglobin)
- Direct Coombs' test (if positive, the antibodies responsible for the positive Coombs' test will be eluted to investigate their specificity (anti-A, anti-B or anti-D)).
- Blood sample for serum IgG.
- Blood samples for enzymes.
- CSM.
- CDASI.

Before, during and after each infusion episode:

- Administration/Infusion of IMP (2.0 g/kg [20 mL/kg] Octagam 10% or placebo given in infusion episodes over 2 to 5 consecutive days).
- Vital signs before, at least once during and at least 1 hour after each infusion episode.

At least 1 hour after the infusion cycle:

- Blood sample for additional safety lab parameters "Panel 2" (serum haptoglobin, hemoglobin, plasma-free hemoglobin, LDH).
- Direct Coombs' test (if positive, the antibodies responsible for the positive Coombs' test will be eluted to investigate their specificity (anti-A, anti-B or anti-D)).
- Wells probability score for DVT. If score is likely for DVT (≥2 points), perform Doppler scan and take blood sample for D-dimers.
- Wells probability score for PE.

In addition, AEs will be monitored and concomitant medications will be documented.

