6.1.4 Visits 4 and 5 (Week 8 and 12; First Period)

The following assessments will be performed:

Before infusion cycle:

- Vital signs.
- Blood sample for safety laboratory (hematology and clinical chemistry).
- Blood sample for serum IgG.
- Blood samples for enzymes.
- CSM.
- CDASI.

Before, during and after each infusion episode:

- Administration/Infusion of IMP (2.0 g/kg [20 mL/kg] Octagam 10% or placebo given in infusion episodes over 2 to 5 consecutive days, or alternate IMP for subjects who deteriorated at 2 consecutive visits).
- Vital signs before, at least once during and at least 1 hour after each infusion episode.

At least 1 hour after the infusion cycle:

- Wells probability score for DVT. If score is likely for DVT (≥2 points), perform Doppler scan and take blood sample for D-dimers.
- Wells probability score for PE.

In addition, AEs will be monitored and concomitant medications will be documented.

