9.2.4 Handling of Missing Data

In general, missing data will not be imputed, with a few exceptions. For ANCOVA analysis of changes from baseline to week 16, LOCF will be used in main model in case of missing values (e.g. due to early termination) and in case of switch to the alternate treatment group (as values obtained after the switch will not be included in the analysis).

For missing weight measurements the last available body weight will be used for all calculations related to dosing (last observation carried forward, LOCF); however, in individual subject data listings missing data will not be replaced by imputed values.

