4.1. Overall Study Design and Plan

Study GAM10-08 is designed as a prospective, parallel group, double-blind, randomized, multicenter phase III study with a 16-week efficacy period followed by a 24-week open-label extension period.

As DM is a rare disease, about 55 sites are projected to participate in countries worldwide with emphasis on (Eastern) European countries and North America. For the same reason, it is not expected that single centers will enroll more than about 5 subjects.

The duration of the entire study for each subject will be up to 43 weeks and consists of the following segments:

- approximately 3 weeks for Screening
- 16 weeks of double-blind treatment
- 24 weeks of open-label treatment with Octagam

[figure not shown]
Eligible subjects after screening will be randomized 1:1 to receive up to four infusion cycles of either 2.0 g/kg Octagam 10% or placebo every 4 weeks during the 16-week First Period. An infusion cycle will consist of 2 to 5 days over which the study drug will be administered.

Subjects, who deteriorate³ in this phase, will be crossed-over to the alternate treatment from week 8 on.

After response assessment at Week 16, the following subject groups will continue in the 6-months open-label Extension Period and receive 2.0 g/kg Octagam 10% given over 2 days (if tolerated by the patient) at 4 week intervals:

- Subjects randomized to Octagam without confirmed deterioration during the First study period including Week 16.
- Subjects randomized to placebo without confirmed deterioration prior to Week 16.
- Subjects randomized to placebo who switched to Octagam and show no further deterioration at Week 16

The rest of the subjects will not continue the study, but Week 16 will be considered as their termination visit:

³ For a definition of confirmed deterioration, please refer to section 8.4.

At Week 28, subjects who are stable on 2.0 g/kg Octagam 10% can be switched to 1.0 g/kg Octagam 10%, at the discretion of the investigator.

Please refer to the study protocol for a detailed flowchart of planned study events and assessments.

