8.3. Handling of Missing Data

In general, missing data will not be imputed, with a few exceptions. For ANCOVA analysis of changes from baseline to week 16, LOCF will be used in main model in case of missing values (e.g. due to early termination) and in case of switch to the alternate treatment group (as values obtained after the switch will not be included in the analysis).

For missing weight measurements the last available body weight will be used for all calculations related to dosing; in individual patient data listings missing data will however not be replaced by imputed values.

No analyses of the patterns of missing data will be done.

For adverse events the following will be applied:

An Adverse Event (AE) is defined as treatment-emergent, if first onset or worsening is after start of the first infusion of Octagam 10% or placebo.

If the start date and time of an AE are partially or completely missing, the AE will be assumed to be treatment-emergent if it cannot be definitely shown that the AE did not occur or worsen during the treatment emergent period (worst case approach). Missing dates and times will not be replaced.

For medications the following will be applied: A medication will be assumed to be concomitant if it cannot be definitely shown that the medication was not administered during the treatment period as defined in section 8.4 below. Missing dates will not be replaced.

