10.2. Secondary efficacy endpoints

All secondary efficacy endpoints will be analyzed and presented in full detail by means of descriptive statistics and inferential analyses as appropriate.

For TIS response at Week 16 by improvement category, the proportion of subjects with at least moderate improvement and the proportion of subjects with major improvement will be calculated together with subject counts and the associated 2-sided 95% confidence interval (CI) for the difference in the proportion of patients with improvement. Moreover, both treatment groups will be compared using a Cochran-Mantel Haenszel test, analogously as for the primary endpoint. The proportion of subjects in each treatment arm who meet confirmed deterioration criteria up to (including) Week 16 will be presented in the same way.

All mean changes to be evaluated as secondary endpoints (listed in section 3.2.2) will be presented by a full set of descriptive parameters: number of subjects with non-missing values, mean, standard deviation, median, minimum and maximum, 1st and 3rd quartile, 95% CI. Moreover, for all continuous secondary endpoints, an analysis of covariance (ANCOVA) will be used to analyze changes from baseline to Week 16. For patients who are switched to the alternate treatment before Week 16, the last value prior to switch will be carried forward to Week 16 and used to calculate change from baseline to Week 16. The model will include treatment and global disease activity as a fixed factor. Center will be included as random factor. The baseline value of the variable to be analyzed will be included as a covariate. Least square means will be derived and presented together with 95%-confidence intervals by treatment group. Moreover, two-sided 95% confidence intervals will be derived for the overall difference in least square means between Octagam and placebo treatment. As sensitivity analysis, a modified ANCOVA model will be used, where the changes from baseline to Week 16 are calculated based on Week 16 values, even if a patient is switched to the alternate

treatment before Week 16. To incorporate the switch into the model, the variable crossover (yes/no) which indicates if there was a switch to the alternate treatment will be included as additional factor into the ANCOVA model, as well as the treatment-by-cross-over interaction term.

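### In the main SF-36v2 ANCOVA, the carry-forward rule gives a change of exactly 0 to every patient switched before Week 16 who has a Week 0 score

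*SAP*

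**What the plan says.** **The rule.** SAP 10.2 and Protocol 9.2.2 apply one main ANCOVA to every continuous secondary endpoint, with no exception for SF-36v2. For patients switched before the Week 16 visit, "the last value prior to switch will be carried forward to Week 16 and used to calculate change from baseline to Week 16". Protocol 9.2.4 says "LOCF will be used in main model in case of missing values", and SAP 8.3 applies the same method "in case of switch to the alternate treatment group (as values obtained after the switch will not be included in the analysis".

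**Who is switched, and when.** Patients with confirmed deterioration are switched. SAP 4.1 says they "will be crossed-over to the alternate treatment from week 8 on". Protocol 3.3.1 says "All subjects in the placebo arm who deteriorate at 2 consecutive visits until Week 8 or after Week 8 will be switched", with the mirror rule in the Octagam arm. Protocol 6.1.4 provides for the alternate product at Weeks 8 and 12.

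**When SF-36v2 is collected.** The row "SF-36 Health Survey" in Protocol Table 1 and the visit lists in Protocol 6.1 place it at Week 0, Week 16 and the Termination or Drop-out visit. It is absent from the lists for Week 4 (6.1.3) and Weeks 8 and 12 (6.1.4). Unscheduled visits (6.1.9) repeat the Week 4 procedures, so it is absent there too.

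**Safeguards.** SAP 10.2 adds a sensitivity ANCOVA on observed Week 16 values with crossover and treatment-by-crossover terms. It also promises further review if more than 10% of patients have missing values or if that second model diverges.

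**The concern.** Carrying the last pre-switch value forward makes sense for a measure taken every four weeks: a patient switched for deterioration keeps a value observed around that deterioration. It fails for a measure with nothing between Week 0 and Week 16, because the value carried forward is then the baseline itself.

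The zeros fall only on patients with confirmed deterioration. In the same analysis such a patient contributes an observed Week 8 or Week 12 value for HAQ and patient global activity, and no change at all for SF-36v2. The main quality-of-life comparison thus holds no post-baseline information from switched patients. If the two arms switch at different rates, the estimated treatment difference can be distorted, and constant zeros also tend to make its standard error too small.

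**Working it through.** **1. The plan's own figures.** The documents give no sample size, SD or switch rate for SF-36v2. The only sample-size figure with inputs is for the primary endpoint: 84 patients, 0.6 v 0.3, 80% power, two-sided 0.05 (SAP 6). It reproduces: [1.960 × √(2 × 0.45 × 0.55) + 0.8416 × √(0.24 + 0.21)]² / 0.3² = 41.97, so 42 per arm and 84 in all. Nothing below depends on it. I use only the planned enrolment of 94, or 47 per arm.

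**2. The rule applied to the schedule.** CSM and CDASI are taken before the infusion, so the assessment at the switch visit counts as pre-switch.

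| Endpoint | Assessed up to Week 16 | Switch at Week 8 | Switch at Week 12 |
|---|---|---|---|
| SF-36v2 | Weeks 0, 16 | Week 0 value carried; change = Y(0) − Y(0) = 0 | Week 0 value carried; change = 0 |
| CSM, CDASI | Weeks 0, 4, 8, 12, 16 | Week 8 value carried | Week 12 value carried |

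The zero holds for every SF-36v2 scale and summary score, in either arm. A switched patient without a Week 0 score has no computable change. Patients whose deterioration is first confirmed at Week 16 are not affected. Nor are unswitched drop-outs who complete SF-36v2 at the Drop-out visit.

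**3. Shift in the treatment difference (illustration).** Let p be the share of an arm that is switched and d the mean worsening in SD that switched patients would have shown at Week 16 without the switch. Scoring them 0 understates the Octagam benefit by pP × dP − pO × dO, where P is placebo and O is Octagam; a negative value means overstated. The unadjusted SE is √(2/47) = 0.206 SD. Every p and d here is my assumption: p from 5% to 30% on placebo and from 2% to 10% on Octagam, d from −0.3 (improvement) to 1.0.

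| Scenario | pP | pO | d, both arms | Shift (SD) | Shift / SE | Patients set to 0 |
|---|---|---|---|---|---|---|
| Low | 5% | 2% | 0.3 | 0.03 × 0.3 = 0.009 | 0.04 | 47 × 0.07 = 3.3 (3.5% of 94) |
| Central | 20% | 5% | 0.5 | 0.15 × 0.5 = 0.075 | 0.36 | 47 × 0.25 = 11.8 (12.5%) |
| High | 30% | 10% | 1.0 | 0.20 × 1.0 = 0.20 | 0.97 | 47 × 0.40 = 18.8 (20%) |

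Extremes with equal d: 0.28 × (−0.3) = −0.084 to 0.28 × 1.0 = +0.28. Extremes with d differing by arm: 0.30 × (−0.3) − 0.10 × 1.0 = −0.19 to 0.30 × 1.0 − 0.10 × (−0.3) = +0.33. Both signs are possible.

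**4. Standard error (unadjusted).** If unswitched patients have mean change m and SD 1, an arm with share p set to 0 has variance (1 − p) + p(1 − p)m². At m = 0 the SE is √([(1 − pP) + (1 − pO)]/47) = 0.2026, 0.1930 and 0.1845 in the three scenarios, which is 1.8%, 6.5% and 10.6% below 0.2063. That is the largest shrinkage. In the central scenario at m = 0.5 the two variances are 0.84 and 0.962, and √(1.802/2) = 0.949, or 5.1%. At m = 1 they are 0.96 and 0.9975, and √(1.9575/2) = 0.989, or 1.1%. Within an arm the reduction vanishes once m reaches 1/√(1 − p), which is 1.12 at p = 20%.

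**5. The 10% trigger.** It needs more than 0.10 × 94 = 9.4 patients. The central and high scenarios pass it only if switched patients count as missing. SAP 10.2 does not say whether they do, and SAP 8.3 lists missing values and switches as separate cases.

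**The case against.** **The outcome is not certain.** The plan does not say that a baseline value may be carried forward. If the programmer decides it may not, switched patients leave the model and there are no zeros. That is true, but nothing in either document bars it, and the text as written yields 0. Dropping the patients would be a different bias that the plan does not choose either.

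**The size is measured against a target that the SAP does not name.** This stands. The shifts use the Week 16 change without a switch, and the switch rates and d are assumed. A reader might infer that the error is known to work against Octagam and is therefore conservative. The documents do not support that: they give no switch rates, and confirmed deterioration can be met on extra-muscular activity alone (Protocol 4.3.1), so SF-36v2 need not have worsened.

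**The standard error need not shrink much.** This also stands. A reader might take 1.8% to 10.6% as expected values. They are the maximum for each scenario, and the planned model adjusts for baseline, disease activity and centre, which these figures do not.

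**A second model and review triggers exist.** They help in part. The second model is only a sensitivity analysis, uses values taken after the alternate treatment, and conditions on crossover, which is itself an outcome of randomised treatment. What counts as divergence is undefined, and no follow-up analysis is named. By-visit tables exclude post-switch values (SAP 7), so they leave these patients out without correcting the estimate.

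**Timing.** SAP 8.4 lets further derivations be described in the study report without amending the SAP. A reader might infer that the handling could be picked after unblinding. SAP 4.3 and 5.1 temper this, because the SAP must be final before the blind is broken.

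**Conclusion.** The point holds. It follows from the stated rule and the visit schedule and needs no outside figure: for SF-36v2, the main ANCOVA assigns a change of exactly 0 to every patient switched before Week 16 who has a Week 0 score. This is a stated rule that gives a wrong result for one endpoint, and the existing safeguards do not repair the main model.

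Its consequence is bounded. SF-36v2 is a secondary, non-confirmatory endpoint. The primary analysis is unaffected, and so are the CSM and CDASI analyses, where the rule carries observed values. The size and direction of the bias are unknown; the ranges in the working show only that, under the assumed inputs, it could run from negligible to about one unadjusted standard error in the three scenarios, and beyond that, in either direction, at the extremes. The standard error will usually be too small, by an amount that shrinks as the mean change in unswitched patients moves away from 0. The change should be made, but nothing else in the analysis depends on it.

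**What to change.** In SAP 8.3 and 10.2, before database lock:

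1. State that the Week 0 SF-36v2 value is not carried forward.
2. For the main SF-36v2 model, treat post-switch SF-36v2 as missing and multiply impute the Week 16 value within randomised arm. Use a short, pre-specified list that is pre-switch for every patient switched at Week 8 or 12: baseline SF-36v2, disease-activity stratum, and HAQ and patient global VAS at Weeks 0, 4 and 8. That is 1 + 2 + 3 + 3 = 9 terms, which about 47 patients per arm must support. Week 12 is left out because it follows the switch for patients switched at Week 8.
3. Name the estimand: Week 16 change had the patient not switched. Note that it differs from the last-value rule kept for CSM and CDASI.
4. Keep the existing model on observed Week 16 values as the sensitivity analysis.
5. State whether switched patients count toward the 10% trigger.

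A simpler acceptable alternative to steps 2 to 4 is to make an analysis of observed Week 16 SF-36v2 by randomised arm the main one for this endpoint.

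**Cost.** SAP wording and a little programming; no new data. The imputation assumes missing at random and extrapolates, because patients with deterioration confirmed by Week 12 are switched. The nearest patients still on assigned treatment are those first confirmed at Week 16, who may be few. It also ignores the Week 12 measures of patients switched at that visit. The alternative avoids these assumptions, but its estimate includes the effect of the alternate treatment.

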3.2.1. Primary Target Variables

The evaluation of the primary endpoint will be based on the newly developed Total Improvement Score (TIS), a scale from 0 to 100, with 20-39 points being minimal improvement, 40-59 points being moderate improvement, and ≥ 60 points being major improvement (Aggarwal et al., 2017, please refer to the protocol for details).

In the context of this study, subjects need to have at least minimal improvement at Week 16 (i.e. $TIS \geq 20$) to qualify as responders.

The primary endpoint is defined as the proportion of responders in the 2.0 g/kg Octagam 10% and placebo arms at Week 16, a responder being defined as a subject with an increase from baseline (Week 0) of ≥ 20 points on the Total Improvement Score (TIS) and who has not met "Confirmed Deterioration" criteria at 2 consecutive visits as defined in Section 8.4 up to (including) Week 16.

The TIS is based on the assessment of six core set measures (CSMs):

1. Physician Global Activity: Global Disease Activity (GDA), assessed by the investigator on a Visual Analog Scale (VAS)
2. Patient Global Activity: GDA, assessed by the patient on a VAS
3. Manual muscle testing: MMT-8 Muscle Grading and Testing
4. Health Assessment Questionnaire (HAQ): Standard HAQ used by the International Myositis Assessment and Clinical Studies Group (IMACS)
5. Enzymes: Aldolase, CK, ALAT, ASAT, LDH
6. Extra muscular activity: Evaluated as part of Myositis Disease Activity Assessment Tool [MDAAT]

Please refer to the protocol for further details and references on these CSMs. The CSMs will be assessed at Screening, at each visit of the first period, at Visit 9 (Week 28), and at the Termination Visit.

The TIS is calculated as a sum of sub-scores as detailed below. The level of improvement will always be based on the comparison of the current CSMs compared to the baseline (Week 0) values.

Core set measure	Level of improvement	Level score
Physician Global Activity	Worsening to 5% improvement	0
	>5% to 15% improvement	7,5
	>15% to 25% improvement	15
	>25% to 40% improvement	17,5
	>40% improvement	20
Patient Global Activity	Worsening to 5% improvement	0
	>5% to 15% improvement	2,5
	>15% to 25% improvement	5
	>25% to 40% improvement	7,5
	>40% improvement	10
Manual muscle testing (MMT)	Worsening to 2% improvement	0
	>2% to 10% improvement	10
	>10% to 20% improvement	20
	>20% to 30% improvement	27,5
	>30% improvement	32,5
Health Assessment Questionnaire (HAQ)	Worsening to 5% improvement	0

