3.2.2. Secondary Target Variables

For Efficacy and Quality of Life (QoL), secondary endpoints will be:

- Proportion of TIS responders by improvement category (minimal, moderate, major) at Week 16 and Week 40.
- Mean change from baseline (Week 0) to end of First Period (Week 16) in modified Cutaneous Dermatomyositis Disease Area and Severity Index (CDASI)
- Mean change from end of First Period (Week 16) to end of Extension Period (Week 40) in modified CDASI.
- Mean change from Baseline (Week 0) to end of First Period (Week 16) and Extension Period (Week 40) in:

- SF-36v2 Health Survey;
- Individual 6 Core Set Measures (CSM) used for TIS calculation.
- Mean TIS from Baseline (Week 0) to end of First Period (Week 16) and from Baseline (Week 0) to end of Extension Period (Week 40).
- Time to minimal, moderate and major improvement in TIS.
- Time to confirmed deterioration (defined on basis of the CSM assessments, see section 8.4 for details) in the First Period and overall.
- Proportion of subjects in each treatment arm who met “confirmed deterioration” criteria up to (including) Week 16

For Safety, target variables will be:

- Occurrence of adverse events (AEs) with an emphasis on thromboembolic events (TEEs) and hemolytic transfusion reactions (HTRs)
- Wells probability scores for deep vein thrombosis (DVT) and pulmonary embolism (PE), and Doppler scan (if indicated)
- Occurrence of all adverse drug reactions (ADRs) and suspected ADRs
- Vital signs (blood pressure, heart rate, body temperature and respiratory rate)
- Physical examination (at Screening and every 12 weeks from Week 4 on)
- Laboratory parameters (hematology, clinical chemistry, IgG, enzymes, viral markers, Coombs' test [plus specific antibodies if positive], D-dimers)
- Pregnancy test

4. Study Methods

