4.3. Randomization, Stratification and Blinding

All subjects qualified to participate in the study at Visit 2 will be randomized to one of the two treatment arms – Octagam 10% or Placebo – in a ratio of 1:1. The randomization scheme will be stratified according to the seriousness of disease before enrollment: Mild | Moderate | Severe.

The Physician's Global Disease Activity assessment will determine the correct stratum for each subject as follows: GDA value of 0-3 [mild], 4-6 [moderate], 7-10 [major]

Within the strata, the same fixed block size will be used for a balanced randomization.

This design will ensure the desired overall randomization ratio and avoid random differences between the treatment groups with respect to the seriousness of DM prior to enrollment.

The randomization scheme will only be available to the statisticians responsible for creating it, and the programmer implementing the scheme into the IRT system. No information on treatment assignment will be communicated to the sponsor or any CRO personnel responsible for the conduct of the study or the analysis of data, with the following exceptions:

- The result of randomization, i.e. the treatment group assignment of individual subjects will be reported to the hospital pharmacist or designee by a dedicated email that no other trial personnel will have access to.
- Subjects with confirmed deterioration who were crossed-over during the First Period and subjects with confirmed deterioration at Week 16 will be unblinded at Week 16 as their further continuation in the Extension Period depends on their initial assignment as described in section 4.1 above. In the analysis of the primary endpoint these subjects will be considered as non-responders in the group they were randomized to.
- In case of medical emergencies as described in the protocol (section 5.6)

Only after completion of all procedures related to data cleaning, the medical review of the data, the finalization of the statistical analysis plan, the agreement on the final subject disposition, and the formal database lock the blind will be broken and the individual treatment assignment will be added to the clinical database for analysis

5. Sequence of Planned Analyses

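### The ANCOVA for mean TIS prescribes a baseline covariate that is 0 for every subject, so the three-level GDA stratum is the only baseline adjustment left

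*SAP*

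**What the plan says.** Mean TIS is a secondary endpoint in SAP 3.2.2 and Protocol 3.1.2, at Week 16 and at Week 40. SAP 10.2 brings it under a general rule: "for all continuous secondary endpoints, an analysis of covariance (ANCOVA) will be used to analyze changes from baseline to Week 16". Treatment and GDA enter that model as fixed effects and study centre as a random effect. On the starting level of each endpoint, the rule is: "The baseline value of the variable to be analyzed will be included as a covariate". Protocol 9.2.2 has the same model, and neither document makes an exception for TIS. The modified ANCOVA planned as sensitivity analysis uses the same base and adds a crossover indicator and its interaction with treatment.

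On the score itself, SAP 3.2.1 says: "The level of improvement will always be based on the comparison of the current CSMs compared to the baseline (Week 0) values". The band worth 0 points is "Worsening to 5% improvement" for five of the six core set measures (CSM); for manual muscle testing its upper limit is 2%.

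The randomisation strata are three bands of Physician's GDA (0-3, 4-6, 7-10) taken before enrolment (SAP 4.3); SAP 8 places that GDA at screening. All six CSM are also recorded at Week 0, before the first infusion (Protocol 6.1.2).

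**The concern.** The evident aim of SAP 10.2 is to adjust each continuous endpoint for where the subject started. That works for CDASI, SF-36v2 and the individual CSM, which all have a baseline that varies between subjects. It cannot work for TIS, which is the continuous form of the measure behind the primary endpoint.

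The retained stratum is a coarse substitute. It is one CSM cut into three bands, measured up to three weeks before the Week 0 values against which TIS is scored, and it holds no direct information on muscle strength. With 94 subjects planned, about 47 per arm, a chance imbalance in baseline strength would be corrected only indirectly. If baseline strength predicts Week 16 TIS within strata, precision is also given away.

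There is a smaller point about pre-specification. SAP 8.4 lets some further derived variables be documented only in the analysis programs, and SAP 13 defers the list of outputs. A covariate put in place of the empty term at that stage would not have been chosen in advance.

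**Working it through.** **The plan's own figure.** The documents give no size, SD or power for the mean-TIS analysis. The only sample-size figure belongs to the primary test (SAP 6: 0.6 vs 0.3, two-sided 0.05, 80% power, total 84). It reproduces: n per arm = [1.960 × √(2 × 0.45 × 0.55) + 0.842 × √(0.6 × 0.4 + 0.3 × 0.7)]² / 0.3² = 42 after rounding up, so 84 in total. Power is 80.0% at 42 per arm and 84.4% at 47. Nothing below changes this.

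**Step 1: TIS at Week 0.** Comparing Week 0 with itself is a 0% change, so all six items fall in their 0 band: TIS = 0 for everyone. The item maxima are 20 + 10 + 32.5 + 10 + 7.5 + 20 = 100. Change in TIS is therefore TIS at Week 16 minus 0, which is TIS at Week 16.

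**Step 2: the model as written.** The fixed-effect columns are intercept, treatment, two stratum indicators and baseline TIS: 5 columns. The last is all zeros, so the rank is 4. Its coefficient is not estimable, and the fit is the one with treatment, stratum and random centre only. The modified ANCOVA inherits the same empty term.

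**Step 3: does baseline limit attainable TIS?** Inputs: MMT-8 runs from 0 to 150 (Protocol 7.2.1), entry requires a score below 142 (Protocol 4.1.1), and the item bands are in SAP 3.2.1. The SAP does not say whether % improvement is relative to the scale range or to the baseline value, so both are shown.

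| Week 0 MMT-8 | Largest gain | % of range | % of baseline | Cap on MMT item (max 32.5) |
|---|---|---|---|---|
| 141 | 9 | 9/150 = 6.0% | 9/141 = 6.4% | 10 on either reading |
| 120 | 30 | 30/150 = 20.0% | 30/120 = 25.0% | 20 or 27.5 |
| 100 | 50 | 50/150 = 33.3% | 50/100 = 50.0% | 32.5 on either reading |

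For MMT-8 the limit holds on either reading. For the VAS items it does not: a Physician Global Activity of 2 cm caps that item at 15 of 20 if scored on the range (2/10 = 20%), but can still earn 20 if scored relative to baseline (up to 100%). HAQ has the same ambiguity.

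**Step 4: what adjustment could gain.** Let ρ be the within-stratum correlation of the added Week 0 covariate(s) with Week 16 TIS. Residual variance is multiplied by 1 − ρ², and the gain is worth 1/(1 − ρ²) − 1 more subjects. ρ is not in the documents, so this range is assumed.

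| ρ (assumed) | Variance reduction | Equivalent extra subjects |
|---|---|---|
| 0 | 0% | 0% |
| 0.2 | 4% | 4% |
| 0.3 | 9% | 10% |
| 0.4 | 16% | 19% |
| 0.5 | 25% | 33% |

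**Step 5: a check on the low end.** An illustrative simulation used 94 subjects, 800 replicates and invented CSM distributions. The share of deficit resolved was drawn independently of baseline, and centre was left out. Five Week 0 CSM were added to the stratum. The mean standard error of the treatment difference went from 4.98 to 4.98 with range scoring, and from 6.11 to 6.23 (2% larger) with baseline-relative scoring. This does not estimate ρ for this trial, and five covariates are more than are proposed here. It shows that a nil gain is plausible.

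**The case against.** The strongest reply is that the empty term does no harm. A constant covariate drops out, and the treatment estimate, least square means and intervals are those of the model without it. SAP 3.2.2 already words the endpoint as a mean TIS rather than a mean change, so naming Week 16 TIS as the response is only clarification. Each CSM is analysed with its own meaningful baseline, and both the logistic sensitivity model for response (SAP 10.1) and the optional Cox models (SAP 10.2) leave room for baseline covariates. All of this stands, although none of those analyses adjusts mean TIS itself.

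It is also fair that a ceiling on one item is not a correlation with the observed score. With the MMT item capped at 10, the rest of the table still allows 20 + 10 + 10 + 10 + 7.5 + 20 = 77.5, above the 60-point threshold for major improvement. That stands too, and is why the assumed range starts at 0.

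A reader might infer that mean TIS gets no baseline adjustment at all. It does get some: GDA, itself a categorised CSM, stays in the model. A reader might also infer that all six CSM bound the score. That is shown only for MMT-8; for the VAS and HAQ items it depends on a scoring convention that the SAP leaves open.

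**Conclusion.** The point holds in a limited form. It follows from the SAP's own definitions that the prescribed baseline covariate for mean TIS is 0 for every subject and cannot be estimated, so adjustment stops at the three-level GDA stratum, with centre as a random term.

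The consequence is modest. On this point the randomised comparison stays unbiased, and the primary test and the sample sizes of 84 and 94 are unaffected. Only precision and chance-imbalance correction on one secondary endpoint are in play. A variance reduction of 0% to 25% rests wholly on an assumed ρ of 0 to 0.5. The documents would not support a claim that precision is demonstrably lost. The case for change is that the plan's intended adjustment fails for this endpoint and can be restored cheaply from data already collected.

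**What to change.** In SAP 10.2, add a rule for TIS, settled before database lock and unblinding:

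- the analysed variable is the Week 16 TIS, with the existing carry-forward rule for switched subjects and missing values unchanged;
- the baseline-TIS term is dropped;
- treatment, GDA stratum and random centre are kept;
- Week 0 MMT-8 is added as a continuous covariate. Continuous Week 0 Physician Global Activity is an optional second one; it overlaps the stratum, so less should be expected of it;
- the modified ANCOVA sensitivity model is changed in the same way.

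Protocol 9.2.2 carries the same general wording, so the SAP should note that this is a TIS-specific clarification of it.

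The cost is a few lines of SAP text, a change to the model statements, and one or two degrees of freedom: of the 94 − 4 = 90 left after the estimable fixed effects (before centre), 89 or 88 remain. No new data are needed.
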